7. DISCONTINUATION FROM STUDY TREATMENT AND FROM THE OVERALL STUDY

Discontinuation of specific study sites is handled as part of the appendix on governance (Section 10.1.9).

Refer to Section 7.4 for criteria that may potentially result in permanent stoppage (discontinuation) of the overall clinical study.

7.1. Discontinuation of Study Intervention

7.1.1. Permanent Discontinuation of a Participant from Study Treatment

It may be necessary for a participant to permanently discontinue from study treatment. If a participant is permanently discontinued from study treatment, that participant will remain in the study to be evaluated for safety follow-up, including survival follow-up. See the SoA (Table 1) for data to be collected at the time of the participant's discontinuation from study treatment and at follow-up, and for any further evaluations that will need to be completed.

A participant's treatment with the IMP (lerociclib) will be permanently discontinued if any of the following events occurs during the study:

- The participant suffers an AE that, in the judgment of the Investigator, Sponsor, or Medical Monitor, presents an unacceptable risk to the participant.
- General or specific changes in the participant's condition (eg, a significant intercurrent illness or complication) that, in the judgment of the Investigator, are unacceptable for further administration of study intervention.
- Change in the participant's compliance with any inclusion/exclusion criterion that is clinically relevant and affects participant safety as determined by the Investigator (or designee).
- Noncompliance with the study restrictions that might affect the participant's safety or the study assessments/objectives, as considered applicable by the Investigator (or designee).
- The participant has any of the following:
 - Serum ALT or AST $> 3 \times$ ULN with the presence of fatigue, nausea, vomiting, right upper quadrant pain, or tenderness, fever, rash, and/or eosinophilia (eosinophil % is $> 5\%$ [eosinophil % = absolute eosinophil count/total white blood cells])
 - Alanine aminotransferase or AST $> 5 \times$ ULN
 - Alanine aminotransferase or AST $\geq 3 \times$ ULN and total bilirubin $\geq 2 \times$ ULN ($> 35\%$ direct bilirubin), OR ALT or AST $\geq 3 \times$ ULN and INR > 1.5 (if INR measured)
- Occurrence of pregnancy in a female study participant or female partner of a male study participant (as applicable).
- Significant noncompliance of the participant with protocol requirements

Note: This includes any participant whose compliance with any study intervention falls below 80%. In such cases, potential discontinuation of the participant from study treatment will be discussed between the Investigator and Sponsor before a final decision is made.

- The Sponsor or legal representative of the Sponsor requests the participant to withdraw.
- The participant has documented disease progression.
- The participant is lost to follow-up.
- The participant exhibits any evidence of drug abuse.
- Permanent study treatment discontinuation is judged by the Investigator to be in the best interest of the participant.
- The participant withdraws consent.
- The Sponsor makes the decision to terminate the site or study.

In the event of a participant discontinuing from IMP (lerociclib) treatment (without withdrawal of consent from the study), that participant should be strongly encouraged to complete all protocol-scheduled assessments—to include the Safety Follow-up Visit 30 days after the last dose of lerociclib and the Post-Treatment Follow-up Phase (which includes a Survival Follow-up Phase that is to continue until at least 50% of enrolled participants have died).

A participant who discontinues from study treatment for reasons other than PD will have a CT or MRI scan performed during the Post-Treatment Visit if that participant has not had a scan performed within the prior 4 weeks.

The Investigator will document the reason for each participant's discontinuation from lerociclib treatment on the applicable eCRF page. When a participant's discontinuation from lerociclib is due to either an SAE or a Grade 3 or 4 toxicity considered to be related to the IMP, the Investigator should follow the event until resolution, stabilization, or it is deemed that further recovery is unlikely. Data on these events should be collected on the AE form in the eCRF.

In the event that a participant discontinues from lerociclib due to an AE or pregnancy, the Investigator should notify the Sponsor Medical Monitor or Pharmacovigilance representative by email within 24 hours of IMP discontinuation.

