6.5. Dose Modification

6.5.1. Lerociclib

A participant may temporarily discontinue from study treatment with lerociclib for a duration of up to 14 days, for any reason. However, any such temporary discontinuations must be reported to the Medical Monitor. Refer to Section [7.1.2](#) for details.

This protocol allows some alteration from the currently outlined lerociclib dosing schedule, but the maximum daily dose will not exceed 300 mg. Dose adjustments of lerociclib for toxicities are to be made according to the organ system showing the greatest degree of drug-related toxicity. Toxicities will be graded using NCI CTCAE v5.0.

No more than 2 lerociclib dose-level reductions in total are allowed for any participant. Toxicity that requires dose-level reduction more than twice will lead to permanent discontinuation of lerociclib dosing for the individual participant. No lerociclib dose re-escalations are allowed if the dose reduction was due to a lerociclib-related toxicity.

In cases where the relationship to lerociclib is unclear, the Investigator may re-challenge the participant after discussion with the Medical Monitor.

Dose reduction will only be performed if the symptom(s) is (are) related to lerociclib in the opinion of the Investigator and not related to the underlying disease. The dose level reductions below will be utilized for the purpose of lerociclib modifications for toxicities.

Table 5: Lerociclib Dose Modifications

| Dose Level | Lerociclib Dose |
|-----------------------|-----------------------|
| Starting dose | 150 mg BID |
| First dose reduction | 100 mg BID |
| Second dose reduction | 50 mg QAM, 100 mg QPM |

BID = twice daily; QAM = once every morning; QPM = once every evening.

An off-drug period of up to 14 days is permitted to allow recovery from any toxicity in order to meet the continuation criteria.

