6.5.1.2. Dose Modifications for Non-hematologic Toxicity

For any non-hematologic toxicity of Grade ≥ 3 severity that persists despite optimal medical treatment, withhold treatment with lerociclib until symptoms resolve to Grade ≤ 2 severity (if not considered a safety risk for the participant). If the treatment interruption duration is > 14 days, approval from the Medical Monitor will be needed to resume treatment.

Treatment should be resumed at the next-lower dose level of lerociclib. If no further dose reduction is possible (participant is already receiving the lowest dose), lerociclib treatment must be discontinued.

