7.1.3. Re-challenge Therapy

Participants may re-challenge therapy for any reason, including toxicity, according to prespecified criteria and with the explicit permission of the Medical Monitor.

If therapy has been stopped due to toxicity, the Investigator must confirm the toxicity is resolving (to at least Grade 2 or better severity) before attempting re-challenge.

If therapy has been discontinued for any other reason, that reason must be provided to the Medical Monitor.

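### Protocol 6.5.1.2 (hold and resume) and 7.1.3 (re-challenge) make no exception for the ALT/AST elevations that 7.1.1 makes a permanent stop

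*Protocol*

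**What the plan says.** Protocol Section 7.1.1 is mandatory: "treatment with the IMP (lerociclib) will be permanently discontinued if any of the following events occurs during the study". One listed event is ALT or AST above 5 × ULN, with no condition on persistence, relatedness, bilirubin, INR or symptoms. Two further liver criteria combine lower ALT/AST elevations with symptoms or eosinophilia, or with raised bilirubin or INR.

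Protocol Section 6.5.1.2 covers any non-hematologic toxicity of Grade 3 or higher "severity that persists despite optimal medical treatment, withhold treatment with lerociclib until symptoms resolve to Grade" 2 or lower. A parenthesis adds "if not considered a safety risk for the participant". It continues: "Treatment should be resumed at the next-lower dose level of lerociclib". The one case in which it requires discontinuation is the lowest dose: "If no further dose reduction is possible (participant is already receiving the lowest dose), lerociclib treatment must be discontinued". Its parent, Section 6.5.1, limits reductions by causality: "Dose reduction will only be performed if the symptom(s) is (are) related to lerociclib in the opinion of the Investigator".

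Protocol Section 7.1.3 reads: "Participants may re-challenge therapy for any reason, including toxicity, according to prespecified criteria and with the explicit permission of the Medical Monitor". It adds: "If therapy has been stopped due to toxicity, the Investigator must confirm the toxicity is resolving", to Grade 2 or better. It does not mention the liver criteria in 7.1.1.

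**The concern.** A site managing a raised ALT or AST is likely to turn first to the dose-modification section. There it finds a complete procedure of hold, recover and resume one level lower, with nothing to say that some ALT/AST elevations fall outside it. If the site follows that procedure, a participant whom 7.1.1 requires to come off lerociclib for good could be dosed again. If the participant has already been stopped, 7.1.3 leaves a route back that does not exclude liver stops.

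What is at stake is the safety of the individual participant and uniform handling across sites, in a trial whose primary objective is safety and tolerability. The same event could also be tabulated as a discontinuation at one site and as an interruption or reduction at another (SAP 4.9.1.3 and 4.9.5), because it was managed differently.

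**Working it through.** The plan states no figure on this point, so the check compares rules.

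**1. Is an ALT/AST elevation within 6.5.1.2?** The section speaks of symptoms resolving, but its scope is any non-hematologic toxicity. Protocol 9.3.3.1 treats laboratory abnormalities as toxicities graded by CTCAE v5.0, and Protocol 10.3.1 counts clinically significant laboratory results as AEs. Nothing removes liver enzymes from its scope. The documents do not reproduce the CTCAE cut-offs, so the comparison is confined to elevations that are both Grade 3 or higher and within a 7.1.1 liver criterion, such as above 5 × ULN.

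**2. What does each section require?** Take a participant whose elevation meets both conditions, persists despite treatment and is judged related to lerociclib. Dose levels are from Protocol Table 5.

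| Current dose | Daily total | 6.5.1.2 | 7.1.1 | Same? |
|---|---|---|---|---|
| 150 mg BID | 150 + 150 = 300 mg | Hold, resume at 100 mg BID | Permanent stop | No |
| 100 mg BID | 100 + 100 = 200 mg | Hold, resume at 50 mg morning, 100 mg evening | Permanent stop | No |
| 50 mg morning, 100 mg evening | 50 + 100 = 150 mg | Discontinue | Permanent stop | Yes |

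The instructions differ at two of the three levels.

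**3. Is precedence stated?** No. Sections 6.5.1.2 and 7.1.1 do not refer to each other. Section 6.5.1 points to 7.1.2 (temporary discontinuation), which is close to 7.1.1 but does not mention the liver criteria. Elsewhere the protocol does write such links: 6.4 points to 7.2.1, and Table 6 sets exceptions to its Grade 3 row.

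**4. Would other provisions catch the case?**

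- Sections 6.5.1 and 7.1.2 require temporary holds to be reported to the Medical Monitor. Within 14 days, however, 7.1.2 leaves the restart to the Investigator's discretion, with notice and not approval.
- Beyond 14 days, 6.5.1.2 requires Medical Monitor approval and 7.1.2 bars a restart, so the exposed window is the first 14 days.
- The 24-hour notice in 7.1.1 is tied to discontinuation for an AE or pregnancy. A site that regards the event as a hold may not apply it.
- Expedited reporting in 8.2.4 needs raised bilirubin or INR as well. An isolated ALT or AST above 5 × ULN does not trigger it.
- Section 8 asks for immediate safety concerns to be discussed with the Sponsor. This is general and sets no threshold.
- The safety-risk parenthesis in 6.5.1.2 is a matter of judgment and names no ALT/AST limit.
- Section 7.1.3 requires Medical Monitor permission and prespecified criteria. The only toxicity criterion it states is resolution to Grade 2 or better.

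These make an inappropriate restart less likely. None states which rule applies.

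**The case against.** The strongest reply is that the rules operate in sequence. Section 7.1.1 applies as soon as a value above 5 × ULN occurs, whereas 6.5.1.2 starts only when a toxicity has persisted despite treatment. By then the participant should already be off lerociclib. The wording also differs in force: 7.1.1 is specific and mandatory, 6.5.1.2 is general and says what should be done, and 7.1.3 is permissive and needs the Medical Monitor's agreement. A site that follows the protocol cannot hold and resume without the Medical Monitor being told.

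Most of this stands. The intended rule is clear, and the oversight is real. It does not remove the conflict, because the sequence protects the participant only if the site consults 7.1.1. A site working from 6.5.1.2 is told to hold only once the toxicity persists, and may then restart within 14 days on notice alone.

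A reader might go further and infer that the protocol authorises dosing after a hepatic stop, or that 6.5.1.2 and 7.1.1 are equally good readings. The documents do not support that: 7.1.1 is unconditional on this criterion, and nothing in 6.5.1.2 or 7.1.3 says that it overrides 7.1.1. A reader might also try to size the problem by the dose a resumed participant would receive, or by one participant's share of a line of therapy. Such figures describe a single hypothetical case at a site that missed a mandatory rule, and they are not evidence of impact.

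**Conclusion.** The point holds as a minor internal conflict bearing on participant safety. Section 6.5.1.2 as written gives the wrong instruction for ALT/AST elevations that 7.1.1 makes a permanent stop, and 7.1.3 does not close the re-challenge route.

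The 6.5.1.2 conflict is narrow: the elevation must meet all the conditions in the check, in a participant above the lowest dose level. It rests on two readings: that liver-enzyme elevations are non-hematologic toxicities under 6.5.1.2, and that some elevations meeting a 7.1.1 liver criterion are also Grade 3 or higher. The documents give no rate of such elevations for lerociclib, so no frequency can be estimated.

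A reader might infer that the primary endpoint or the SAP is compromised. It is not. The incidence of AEs and SAEs is defined independently of this rule, and the SAP summaries of discontinuations, interruptions and reductions are correctly specified whichever action a site takes.

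**What to change.** Two short additions at the next protocol amendment:

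- In 6.5.1.2, after the opening scope: *except ALT/AST elevations meeting the Section 7.1.1 criteria, for which lerociclib is permanently discontinued*.
- In 7.1.3: *re-challenge is not permitted after permanent discontinuation under the Section 7.1.1 hepatic criteria*.

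Sections 7.1.1 and 7.1.2 and the SAP need no edit for this point. The stopping rule itself does not change; it becomes visible where sites look up dosing. The cost is the drafting, with no added visits, data, tables or participants.

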7.1.2. Temporary Discontinuation of a Participant from Study Treatment

A participant may temporarily discontinue from study treatment for a duration of up to 14 days, for any reason. However, any such temporary discontinuations must be reported to the Medical Monitor and study assessments must continue as specified in the SoA.

If the IMP (lerociclib) is temporarily discontinued for any study participant, it may be restarted within the aforementioned 14-day period under the discretion of the Investigator with notice to the Medical Monitor. Beyond a duration of 14 days, the participant may not re-start lerociclib therapy and will be removed from the study.

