| FSH Measurement (Female Participants of Non-Childbearing Potential Only) | X | | | | | | | | |
| 12-Lead ECG ^e | X ^b | X | X | X | X | X (at Cycles 4 and 5 only) | X | | |
| ECHO or MUGA with EF | | As clinically indicated by Investigator | | | | | | | |
| Vital Signs | X | X | X | X | X | X | X | | |
| PK Sampling ^f | | X | X | X | X | X (at Cycles 4 and 5 only) | | | |
| Tumor Evaluation (per RECIST v1.1) | X | Every 8 weeks (± 7 days) during the first 12 months and every 12 weeks (± 7 days) thereafter until disease progression, death, withdrawal of consent, loss to follow-up, or participant/legally acceptable representative decision, and at EOT/ED (as applicable). If PR/CR is reported, confirmation of response is required; confirmatory assessment should be performed ≥ 4 weeks after response is first documented. ¹ | | | | | | | |
| Whole-Body Bone Scan ^g | X | Every 8 weeks (± 7 days) for the first 12 months, then: -If initial bone scan is positive for bony lesion, every 12 weeks thereafter, OR -If initial bone scan is negative for bony lesion, bone scan can be done annually or per Investigator standard of care. | | | | | | | |

| Procedure | Screening | Treatment Phase | | | | | | Post-Treatment Follow-up Phase | |
|---|--|--|--|----------|----------|-------------------|--|-----------------------------------|--------------------------|
| | | Cycle 1 | | Cycle 2 | Cycle 3 | Subsequent Cycles | EOT/ED (as applicable) | Safety Follow-up | Survival Follow-up Phase |
| Study Day(s) | D-42 to D-1 | D1 | D15 | D1 | D1 | D1 | Within 15 days after last dose of lerociclib | Last dose of lerociclib + 30 days | Every 12 weeks |
| Visit Window (days) | - | - | ± 2 days | ± 2 days | ± 2 days | ± 2 days | - | + 5 days | ± 7 days |
| Lerociclib Administration/Accountability | | Twice daily continuously in 28-day cycles ^a | | | | | | | |
| Letrozole Administration ⁱ | | Once daily continuously in 28-day cycles | | | | | | | |
| Fulvestrant Administration ⁱ | | X | X | X | X | X | | | |
| Goserelin Administration ^j | X (goserelin dosing required for ≥ 28 days prior to study entry) | X (determined as date of participant's last goserelin dose + 28 days ^l) | q28d after goserelin C1D1 for the individual participant | | | | | | |
| AE/SAE Review | X (continuous from Screening through 30 days after last study intervention dose) | | | | | | | | |

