While receiving lerociclib, participants will undergo imaging assessments (via CT of the chest/abdomen/pelvis with contrast or MRI with gadolinium) every 8 weeks for the first 12 months, then every 12 weeks thereafter. All participants will undergo a bone scan at baseline and annually thereafter (or as per the Investigator's standard of care). If bone disease is identified, participants will require whole-body bone scans every 8 weeks for the first 12 months and then every 12 weeks thereafter.

Optional imaging modalities include a brain CT/MRI (if brain lesion[s] indicated at Screening), CT/MRI for any disease outside the chest/abdomen/pelvis (if lesion[s] identified at Screening), or skin color photography (if skin lesion[s] identified at Screening) every 8 weeks during the first 12 months, then every 12 weeks thereafter.

Participants will continue therapy until disease progression as determined by the Investigator per RECIST v 1.1, unacceptable toxicity, withdrawal of consent, start of a new anticancer treatment, discontinuation of the participant by the Investigator, or termination of the study by the Sponsor, whichever occurs first.

Following disease progression, participants will only be followed for survival, and will no longer require any scheduled assessments beyond that timepoint. Survival status will be assessed every 12 weeks regardless of the participant's reason for discontinuing study treatment.

Safety monitoring (AE/SAE monitoring, clinical laboratory tests, vital signs, 12-lead ECGs, physical examination), serial blood samples for PK, tumor biopsies, and bone scans will be performed at the timepoints specified in the study SoA ([Table 1](#)).

The study is anticipated to last for a total of approximately 48 months. This assumes 12 months to complete participant recruitment and a median PFS of 24 months, plus an additional 12 months for further monitoring.

An independent DSMB will be set up to periodically review and evaluate the accumulated study data for participant safety and for study conduct and progress, and to make recommendations to the Sponsor concerning the continuation of the study (as detailed in [Section 7.4](#)).

This study will be conducted in compliance with the protocol, GCP, and applicable regulatory and IRB/IEC requirements.

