CYP2C8 Inhibitors and Inducers

Lerociclib is a substrate for CYP2C8, although the extent of metabolism by CYP2C8 is expected to be low in humans since the in vitro clearance of lerociclib in human liver microsomes and hepatocytes was low. Lerociclib exposure may be altered by concomitant use of drugs that are strong CYP2C8 inhibitors or inducers.

- **Caution should be exercised** with concomitant use of drugs that are strong inhibitors of CYP2C8 (eg, gemfibrozil, quercetin, sulfapyrazone, trimethoprim, and nicardipine).
- **Monitor for efficacy** with concomitant use of drugs that are strong or moderate inducers of CYP2C8 (eg, rifampin, phenobarbital, and carbamazepine).

Bisphosphonates and Denosumab

Bisphosphonates and denosumab for the treatment of osteoporosis or management of existing bone metastases may be continued for participants who have been receiving them at a stable dose for at least 14 days prior to first dose of lerociclib.

However, the need to initiate or increase the dose of these therapies during the study will be considered as indicative of disease progression leading to the discontinuation of participant from the study unless disease progression can be completely ruled out and the exact reason for the use of these therapies is clearly documented in the participant's source documentation. Such cases must be discussed with the Medical Monitor first.

Medications Not Recommended

Chronic immunosuppressive therapies should be avoided, including systemic corticosteroids. Steroids given for physiological replacement, as anti-emetics or by inhalation, as well as short course of oral/topical steroids given for allergic reactions or asthma flares are allowed.

Any use of systemic corticosteroids for reasons other than those mentioned above shall be discussed with the Medical Monitor prior to use.

The use of herbal medicine is not recommended.

Additional Cautions

Lerociclib inhibited P-gp, BCRP, MATE1, MATE2-K, and OCT1 and OCT2 membrane transporters and therefore caution should be exercised with concomitant use of drugs that are substrates for these transporters. MATE2-K is involved with tubular secretion of creatinine and inhibition of MATE2-K by lerociclib may cause an increase in serum creatinine levels unrelated to true changes in renal function.

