Nontarget lesions: All other lesions (or sites of disease) identified at baseline should be identified as nontarget lesions and recorded in the eCRF. Measurements of these lesions are not required, but the presence, absence, or unequivocal progression of each nontarget lesion should be recorded in the eCRF at each follow-up timepoint. Multiple nontarget lesions in the same organ may be noted as a single item on the eCRF.

New Lesions

Any new lesions should be identified and recorded at each follow-up assessment, as these are markers of disease progression. As defined in the RECIST v1.1 Guidelines ([Eisenhauer 2009](#)), new lesions include the following:

- A lesion in an anatomical location that was not scanned at baseline
- Equivocal new lesion of small size that with continued therapy and follow-up is found to progress and represent new disease (progression should be considered as of the date of the initial scan)
- Negative PET with FDG-PET at baseline, but has a positive FDG-PET at follow-up

No FDG-PET at baseline and a positive FDG-PET at follow-up that corresponds to a new site of disease as confirmed by CT (date of disease progression should be the date of the initial abnormal FDG-PET scan).

The need to initiate or increase the dose of a bisphosphonate and/or denosumab during the study **will be considered as indicative of clinical disease progression** leading to the discontinuation of participant from the active treatment phase **unless** disease progression can be completely ruled out and the exact reason for the use of these therapies is clearly documented in the participant's source documentation. All such cases must be first discussed with the Medical Monitor.

Note: Findings attributable to differences in scanning technique or a change in type of imaging (CT versus MRI) and findings representing something other than tumor (eg, healing or flare of existing bone lesions, necrosis of a liver lesion) should not be considered new lesions.

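### Protocol 7.1.2 and 6.9 take participants out of the study in situations where 7.1.1, 4.1 and 8.1.1.1 end only treatment

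*Protocol*

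**What the plan says.** **Long interruptions.** Protocol 7.1.2 allows lerociclib to be interrupted for up to 14 days. It then states: "Beyond a duration of 14 days, the participant may not re-start lerociclib therapy and will be removed from the study". Protocol 7.1.1 covers permanent discontinuation from treatment and says "that participant will remain in the study to be evaluated for safety follow-up, including survival follow-up". It also strongly encourages such participants to complete the scheduled assessments, including the Safety Follow-up Visit and the Survival Follow-up Phase. Protocol 4.1 adds: "Survival status will be assessed every 12 weeks regardless of the participant's reason for discontinuing study treatment". SAP 3.1 and 3.1.2 repeat that rule.

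**Bone agents.** Both 6.9 and 8.1.1.1 treat the need to start or increase a bisphosphonate or denosumab as a sign of progression, unless progression is excluded and the reason documented. The stated consequence differs. In 6.9 it is "leading to the discontinuation of participant from the study unless disease progression can be completely ruled out". In 8.1.1.1 it is "leading to the discontinuation of participant from the active treatment phase".

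**Restart.** 7.1.2 bars restart after 14 days. Section 6.5.1.2 allows it after a longer interruption for non-hematologic toxicity if the Medical Monitor approves. Section 7.1.3 allows re-challenge for any reason with the Medical Monitor's explicit permission.

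**Imaging after lerociclib.** Section 4.1 ties scans to treatment ("While receiving lerociclib, participants will undergo imaging assessments"). Section 7.1.1 provides one post-treatment scan ("A participant who discontinues from study treatment for reasons other than PD will have a CT or MRI scan performed", if there was none in the prior 4 weeks). The Schedule of Activities (SoA) runs tumour evaluation "thereafter until disease progression, death, withdrawal of consent, loss to follow-up, or participant/legally acceptable representative decision".

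**The concern.** Stopping a drug and leaving a study have different consequences for the data. Someone who only stops lerociclib still contributes safety, survival and possibly tumour data. Someone removed from the study contributes nothing further unless the site goes beyond what it was told to do.

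Two sentences in the current text order the second outcome where other sections order the first. Under 7.1.2 the people affected are those with long interruptions. The documents do not say why such interruptions would occur, but toxicity is one obvious reason, and safety is the primary objective. Under 6.9 they are people judged to have progressed, for whom 4.1 keeps survival follow-up only. The loss under 6.9 is therefore survival contacts, not scans.

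**Working it through.** **1. Could the removal wording mean removal from treatment?** The first half of the 7.1.2 sentence already ends treatment by barring restart. If the second half meant the same, it would add nothing. Protocol 7.2 separates the two ideas, since a participant who leaves the study ends both the interventions and the overall study. Protocol 10.1.11 tells sites to follow the protocol exactly. Read as written, 7.1.2 therefore adds a study exit that 7.1.1 and 4.1 exclude.

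**2. The sections side by side**

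| Event | Text that ends study participation | Text that ends only treatment |
|---|---|---|
| Off lerociclib for more than 14 days | 7.1.2 | 7.1.1; 4.1 (survival every 12 weeks) |
| Bone agent started or increased, progression not excluded | 6.9 | 8.1.1.1; 4.1 (survival follow-up after progression) |

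**3. What literal compliance would cost**

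- *OS.* Survival contacts stop. SAP 4.10.3.3 censors at the last date known alive.
- *Safety (7.1.2 only).* The rule takes effect after day 14 off drug. The Safety Follow-up Visit is 30 days after the last dose, and the treatment-emergent window in SAP 4.9.1.3 also runs to 30 days after end of treatment. If removal is handled as study withdrawal, 7.2.1 asks for clinical follow-up of ongoing non-serious or unrelated serious events only to 14 days after the last dose, which has already passed. Adverse event review in the SoA and serious event reporting in 8.3.4 still run to 30 days, so the site holds conflicting instructions.
- *PFS (7.1.2 only).* SAP 4.10.3.2 uses scans taken after lerociclib ends, provided no earlier censoring event has occurred. Any such scan is lost on removal.

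**4. Size**

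The plan gives no figure for this rule. Its one precision figure concerns ORR: a 95% half-width of about 16% with about 40 participants with measurable disease per line. That reproduces. The normal approximation gives 1.96 × √(0.25/40) = 15.5%. The exact interval at 20/40 is 33.8% to 66.2%, a half-width of 16.2%. The present point does not touch it.

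For PFS and OS the planned number is about 50 per line. Suppose *m* participants have unknown status at a landmark and all others are known. The event-free proportion then lies in an interval of width *m*/50, with no hazard assumption:

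- *m* = 1: 2 points
- *m* = 3: 6 points
- *m* = 5: 10 points

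The values of *m* are illustrative. For scale, the 95% half-width at a proportion of 50% is 1.96 × √(0.5 × 0.5/50) = 13.9 points.

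Survival contacts forgone per removal have an upper bound. Contacts start after the safety visit (30 days after last dose) and recur every 84 days. With potential follow-up *F* months and last dose at month *r*, the count is floor(((*F* − *r*) × 30.4375 − 30)/84). The 48-month study and 12-month recruitment give *F* = 48 for the first participant enrolled and 36 for the last. The range *r* = 1 to 12 is assumed.

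- *F* = 36: *r* = 1 gives 12; *r* = 12 gives 8.
- *F* = 48: *r* = 1 gives 16; *r* = 12 gives 12.

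The bound is therefore 8 to 16 contacts, for a participant who lives to study end.

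**The case against.** **Intent is recoverable.** Section 7.1.2 sits under the heading on discontinuing study intervention. Study withdrawal has its own section, 7.2.1, whose open-ended list of reasons does not name a long interruption. The rule to keep following participants is stated in the synopsis, 4.1, 7.1.1, SoA footnote k and the SAP. For bone agents, 8.1.1.1 gives the rule in nearly the same words as 6.9. A careful site could work out what was meant. This stands as evidence of intent, and it supports treating the matter as a wording fault. It does not remove the contradiction, for the reasons in step 1 of the working.

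**The loss may be small.** Section 7.3 provides for collecting vital status, including from public sources, in wording broad enough to cover all enrolled participants, so some survival data may be recoverable. In the earlier study described in 4.3, Grade 3 neutropenia without fever required no interruption or reduction, and two participants at 150 mg twice daily had dose reductions. That is not a rate of interruptions beyond 14 days, but it gives no sign that they are common. Both points stand.

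**Stronger readings the documents do not support.** A reader might count every remaining SoA scan up to progression as forgone after a 7.1.2 removal. The protocol does not settle whether those scans are due, since 4.1 and 7.1.1 point one way and the SoA the other. SAP Table 2 also censors PFS at the start of new antineoplastic therapy, so scans after a switch would add nothing. A reader might also infer that removal biases PFS or OS in a known direction. The documents give neither the reasons for long interruptions nor the later prognosis of those affected, so no direction can be assigned.

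**Conclusion.** The inconsistency is real and in the current text. As written, 7.1.2 conflicts with 7.1.1 and 4.1, and 6.9 conflicts with 8.1.1.1. Followed literally, both end survival contacts. Section 7.1.2 can also end follow-up before the 30-day safety visit and lose any post-treatment scans the SAP would use.

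The effect is bounded and probably modest unless many participants are removed: at most 2 points of added uncertainty in a landmark proportion per participant of unknown status, assuming 50 per line. How many would be affected cannot be derived from the documents. PFS and OS are secondary, and no hypothesis is tested. It should be corrected because follow-up stopped early may not be recoverable and the correction is cheap.

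**What to change.** **Protocol 7.1.2.** Replace the last sentence with: *Beyond 14 days, lerociclib may be restarted only with Medical Monitor approval (6.5.1.2, 7.1.3); otherwise the participant is permanently discontinued from lerociclib and remains in the study for safety and survival follow-up and the post-treatment assessments in 7.1.1 and the SoA, unless consent is withdrawn.* This also removes the conflict over restart, because approval and permanent discontinuation become alternatives.

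**Protocol 6.9.** Replace discontinuation from the study with discontinuation from the active treatment phase, as in 8.1.1.1, and state that survival follow-up continues.

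**Cost.** A wording amendment or clarification, plus contacts already scheduled in the SoA. The SAP needs no change. The 7.1.2 text refers to 7.1.1 and the SoA for assessments and so does not itself decide how long imaging continues after lerociclib. That remains a separate choice for the sponsor.
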